### 4.2. Inclusion Criteria

Subjects must meet **all** of the following inclusion criteria to be eligible for participation in this study.

- 1) The ability to understand and sign a written informed consent form, which must be obtained prior to initiation of study procedures
- 2) Female, (at birth), Age  $\geq$  18 years
- 3) Currently on a stable antiretroviral regimen of E/C/F/TAF, E/C/F/TDF, or ATV+RTV+FTC/TDF continuously for  $\geq$  12 consecutive weeks preceding the screening visit
- 4) Completion of the Week 48 OLE visit or any post Week 48 OLE visits in study GS-US-236-0128, completion of the Week 96 visit or any post Week 96 visits in study GS-US-292-0109, or completion of the Week 144 visit or any post Week 144 visits in studies GS-US-292-0104 or GS-US-292-0111
- 5) Documented plasma HIV-1 RNA levels  $<$  50 copies/mL for  $\geq$  12 weeks preceding the Screening Visit. After reaching HIV-1 RNA  $<$  50 copies/mL, single values of HIV-1 RNA  $\geq$  50 copies/mL followed by resuppression to  $<$  50 copies/mL are allowed
- 6) HIV-1 RNA  $<$  50 copies/mL at screening
- 7) Normal ECG (or if abnormal, determined by the Investigator to be not clinically significant)
- 8) Adequate renal function:  
Estimated glomerular filtration rate  $\geq$  50 mL/min ( $\geq$  0.83 mL/sec) according to the Cockcroft-Gault formula [{Cockcroft et al 1976}](#):

$$\frac{(140 - \text{age in years}) \times (\text{wt in kg})}{72 \times (\text{serum creatinine in mg/dL})} \times 0.85 = \text{CrCL (mL/min)}$$

$$\frac{(140 - \text{age in years}) \times (\text{wt in kg}) \times 0.85}{72 \times (\text{serum creatinine in } \mu\text{mol/L}) \times 0.6786} = \text{CrCL (mL/sec)}$$

- 9) Hepatic transaminases (AST and ALT)  $\leq 5 \times$  upper limit of normal (ULN).
- 10) Total bilirubin  $\leq 1.5$  mg/dL ( $\leq 26 \mu\text{mol/L}$ ), or normal direct bilirubin.

- 11) Adequate hematologic function (absolute neutrophil count  $\geq 750/\text{mm}^3$  ( $\geq 0.75 \text{ GI/L}$ ); platelets  $\geq 50,000/\text{mm}^3$  ( $\geq 50 \text{ GI/L}$ ); hemoglobin  $\geq 8.5 \text{ g/dL}$  ( $\geq 85 \text{ g/L}$ )).
- 12) Serum amylase  $\leq 5 \times \text{ULN}$  (subjects with serum amylase  $> 5 \times \text{ULN}$  will remain eligible if serum lipase is  $\leq 5 \times \text{ULN}$ ).

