#### 7.5.6. Management of Hyperbilirubinemia

Most patients taking atazanavir sulfate experience asymptomatic elevations in indirect (unconjugated) bilirubin related to inhibition of UDP-glucuronyl transferase (UGT). Hepatic transaminase elevations that occur with hyperbilirubinemia should be evaluated for alternative etiologies. Dose modification of atazanavir sulfate is not permitted. Subjects who experience unacceptable jaundice/scleral icterus can be discontinued from study at the discretion of the Investigator.

- Subjects with bilirubin levels of  $5-10 \times$  ULN, if isolated and not accompanied by unacceptable clinical jaundice (scleral icterus or cutaneous jaundice) may continue on study, if agreed upon by the subject and the Investigator. All subjects with serum bilirubin levels  $5-10 \times$  ULN must have bilirubin, AST and ALT repeated at least once within 7 days of the Investigator being notified of the elevated bilirubin level. Thereafter, serum bilirubin levels  $5-10 \times$  ULN without clinically significant elevation in AST or ALT should be followed according to the clinical judgment of the Investigator.
- Subjects whose hyperbilirubinemia ( $5-10 \times$  ULN) is accompanied by  $\geq$  Grade 2 ALT or AST elevation or who experience a one Grade worsening in ALT or AST do not qualify as having isolated hyperbilirubinemia and will be discontinued.
- Confirmed hyperbilirubinemia  $> 10 \times$  ULN will require discontinuation.
- Elevation of conjugated (direct) bilirubin  $> 2$  mg/dL in association with Grade 2 ALT or AST elevation will require discontinuation.

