Hyperuricemia	>ULN to 10.0 mg/dL >ULN to 597 µmol/L	> 10.0 to 12.0 mg/dL > 597 to 716 µmol/L	> 12.0 to 15.0 mg/dL > 716 to 895 µmol/L	> 15.0 mg/dL > 895 µmol/L
Hypouricemia Adult and Pediatric ≥ 1 year	1.5 mg/dL to < LLN 87 µmol/L to < LLN	1.0 to < 1.5 mg/dL 57 to < 87 µmol/L	0.5 to < 1.0 mg/dL 27 to < 57 µmol/L	< 0.5 mg/dL < 27 µmol/L
Infant < 1 Year	N/A	1.0 mg/dL to < LLN- 57 µmol to < LLN	0.5 to < 1.0 mg/dL 27 to < 57 µmol/L	< 0.5 mg/dL < 27 µmol/L
Creatinine**	> 1.50 to 2.00 mg/dL > 133 to 177 µmol/L	> 2.00 to 3.00 mg/dL > 177 to 265 µmol/L	> 3.00 to 6.00 mg/dL > 265 to 530 µmol/L	> 6.00 mg/dL > 530 µmol/L

CHEMISTRY				
	Grade 1	Grade 2	Grade 3	Grade 4
Bicarbonate Adult and Pediatric ≥ 4 Years	16.0 mEq/L to < LLN 16.0 mmol/L to < LLN	11.0 to < 16.0 mEq/L 11.0 to < 16.0 mmol/L	8.0 to < 11.0 mEq/L 8.0 to < 11.0 mmol/L	< 8.0 mEq/L < 8.0 mmol/L
Pediatric < 4 Years	NA	11.0 mEq/L to < LLN 11.0 mmol/L to < LLN	8.0 to < 11.0 mEq/L 8.0 to < 11.0 mmol/L	< 8.0 mEq/L < 8.0 mmol/L
Triglycerides (Fasting)	NA	500 to 750 mg/dL 5.64–8.47 mmol/L	> 750 to 1200 mg/dL > 8.47–13.55 mmol/L	> 1200 mg/dL > 13.55 mmol/L
LDL (Fasting) Adult	130 to 160 mg/dL 3.35 to 4.15 mmol/L	>160 to 190 mg/dL >4.15 to 4.92 mmol/L	> 190 mg/dL >4.92 mmol/L	NA
LDL (Fasting) Pediatric >2 to <18 years	110 to 130 mg/dL 2.84 to 3.37 mmol/L	>130 to 190 mg/dL >3.37 to 4.92 mmol/L	> 190 mg/dL >4.92 mmol/L	NA
Hypercholesterolemia (Fasting)	200 to 239 mg/dL 5.16 to 6.19 mmol/L	> 239 to 300 mg/dL > 6.19 to 7.77 mmol/L	> 300 mg/dL > 7.77 mmol/L	NA
Pediatric < 18 Years	170 to 199 mg/dL 4.39 to 5.15 mmol/L	> 199 to 300 mg/dL > 5.15 to 7.77 mmol/L	> 300 mg/dL > 7.77 mmol/L	NA
Creatine Kinase	3.0 to < 6.0 × ULN	6.0 to < 10.0 × ULN	10.0 to < 20.0 × ULN	≥ 20.0 × ULN

\* Calcium should be corrected for albumin if albumin is < 4.0 g/dL

\*\* An overlap between the Grade 1 scale and the Lab's normal range for creatinine may result for Male subjects > 70 yrs. Please follow the Gilead convention of grading any result within the LLN and ULN a 0.

ENZYMES				
	Grade 1	Grade 2	Grade 3	Grade 4
AST (SGOT)	1.25 to 2.50 × ULN	> 2.50 to 5.00 × ULN	> 5.00 to 10.00 × ULN	> 10.00 × ULN
ALT (SGPT)	1.25 to 2.50 × ULN	> 2.50 to 5.00 × ULN	> 5.00 to 10.00 × ULN	> 10.00 × ULN
GGT	1.25 to 2.50 × ULN	> 2.50 to 5.00 × ULN	> 5.00 to 10.00 × ULN	> 10.00 × ULN

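### Inclusion criteria 9 and 10 can admit a woman whose entry bilirubin and transaminases already fall under a required discontinuation in Section 7.5.6

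*Protocol*

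**What the plan says.** Protocol Section 4.2 sets two hepatic limits for entry. Criterion 9 accepts AST and ALT up to 5 × ULN. Criterion 10 accepts total bilirubin up to 1.5 mg/dL, "or normal direct bilirubin". That second alternative puts no limit on total bilirubin. Criterion 3 requires women to be "Currently on a stable antiretroviral regimen of E/C/F/TAF, E/C/F/TDF, or ATV+RTV+FTC/TDF continuously for" at least 12 weeks before screening, so women on atazanavir are screened while taking it.

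Section 7.5.6 opens by saying that most patients on atazanavir have symptom-free rises in indirect bilirubin, through inhibition of UGT. Its bullets then set these rules:

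- Bilirubin 5–10 × ULN, isolated and without unacceptable jaundice: the woman may continue if she and the investigator agree.
- Bilirubin 5–10 × ULN with at least "Grade 2 ALT or AST elevation or who experience a one Grade worsening in ALT or AST": such women "do not qualify as having isolated hyperbilirubinemia and will be discontinued".
- Confirmed bilirubin above 10 × "ULN will require discontinuation", with no transaminase condition.
- Direct bilirubin above 2 mg/dL with Grade 2 ALT or AST: discontinuation.

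Appendix 4 defines Grade 2 for both ALT and AST as "> 2.50 to 5.00 × ULN". Sections 4.2 and 7.5.6 do not refer to each other.

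**The concern.** Entry limits and stopping limits should not contradict each other at the moment of enrolment. Here a site could correctly enrol and dose a woman, and the next section would then direct that she be discontinued for a value she arrived with. The site cannot satisfy both sections. Because the trial is open label, a site settling the matter case by case would know her arm.

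At stake are avoidable discontinuations and their effect on the Week 48 tables. Under the snapshot algorithm (Section 8.5.1.1), a woman who stops study drug for a reason other than lack of efficacy, whose last on-treatment HIV-1 RNA is below 50 copies/mL and who has no on-treatment value in the window, is classed as having no virologic data. Attending later visits does not change this, because on-treatment data end 1 day after the last dose. She then counts against her arm on discontinuations and on the secondary endpoint.

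**Working it through.** **The plan's own design figure.** Section 8.8 states at least 87% power with 235 per arm, 2% in both arms, a 4% margin and one-sided 0.025. By the normal approximation the standard error is √(2 × 0.02 × 0.98 / 235) = 0.0129, and Φ(0.04 / 0.0129 − 1.96) = 0.872. The figure reproduces. The present point does not depend on it; only the 235 is used below.

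**Entry set against stop set.** I read bilirubin in 7.5.6 as total bilirubin and discontinuation as stopping study drug.

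- Eligible: AST and ALT ≤ 5 × ULN, and either total bilirubin ≤ 1.5 mg/dL or normal direct bilirubin.
- Stop A: bilirubin 5–10 × ULN with ALT or AST above 2.5 × ULN (Grade 2 or higher).
- Stop B: confirmed bilirubin above 10 × ULN.

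The one-Grade-worsening trigger needs a change after entry, so it is left out.

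Criterion 9 contains the whole Grade 2 band, since both end at 5 × ULN. The documents give no ULN for bilirubin in mg/dL, so I assume 1.0 to 1.3 mg/dL. A grid over total bilirubin, transaminases and direct bilirubin (normal or not) gives an overlap at every ULN tried:

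| Assumed ULN (mg/dL) | Total bilirubin for stop A, with ALT or AST > 2.5 to 5 × ULN | Total bilirubin for stop B, eligible at any admissible ALT and AST |
|---|---|---|
| 1.0 | 5.0–10.0 mg/dL | > 10.0 mg/dL |
| 1.1 | 5.5–11.0 mg/dL | > 11.0 mg/dL |
| 1.2 | 6.0–12.0 mg/dL | > 12.0 mg/dL |
| 1.3 | 6.5–13.0 mg/dL | > 13.0 mg/dL |

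All of the overlap comes through the normal-direct-bilirubin alternative. A total of 1.5 mg/dL is only 1.15 to 1.5 × ULN here; it would reach 5 × ULN only if the ULN were 1.5 / 5 = 0.3 mg/dL. Stop B needs criterion 10 alone.

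The direct-bilirubin stop is not met at entry. A woman admitted on total ≤ 1.5 mg/dL cannot have direct bilirubin above 2 mg/dL. One admitted on normal direct bilirubin does not either, assuming 2 mg/dL lies above the normal range.

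**Could the values be confirmed at entry?** Bilirubin, AST and ALT are measured at Screening (6.2.1) and at Day 1 (6.2.2), up to 30 days apart. Two concordant results could therefore exist by the first dose.

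**Effect on endpoints.** Each suppressed woman moved to no virologic data lowers her arm's rate below 50 copies/mL by 1/235 = 0.43 points. The documents give no count, so the numbers of women in one arm are assumed: 2 give 0.85 points, 5 give 2.13 and 10 give 4.26. The secondary margin is 10 points (8.5.2). She adds nothing to the primary numerator of HIV-1 RNA ≥ 50 copies/mL.

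**The case against.** **The rules are coherent for isolated indirect hyperbilirubinaemia of 5–10 × ULN.** The direct-bilirubin alternative fits the bullet that lets such women continue. This stands, and it confines the conflict to two groups: 5–10 × ULN with Grade 2 transaminases, and above 10 × ULN.

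**A single screening value does not compel a stop.** The rule above 10 × ULN needs confirmation. The 5–10 × ULN band calls for repeat bilirubin, AST and ALT within 7 days. Section 7.5 also asks that clinically significant Grade 3 and 4 results be repeated before drug is stopped, and bilirubin above 5 × ULN is Grade 4. This stands as a qualification, but confirmation delays the conflict and does not remove it.

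**Other safeguards may apply.** Exclusion 8 (investigator judgement) and exclusion 13 (acute hepatitis) could remove some women, but neither sets a bilirubin limit. Section 7.1.1 keeps unchanged pre-existing abnormalities from being adverse events; it does not lift the stops in 7.5.6. The content of Appendix 3, to which Section 7.5 refers, is not in the text available here, so the absence of an allowance for entry values is established only for the visible sections.

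**A stronger reading is tempting.** A reader might infer that the stop persists only in women randomised to stay on atazanavir, and so biases the comparison toward GS-9883/F/TAF. The inference has some basis: 7.5.6 attributes the bilirubin rise to atazanavir, and Section 1.2.2.1 reports no inhibition of UGT1A1 by GS-9883 up to 25 µM. If bilirubin fell below 5 × ULN after the switch, stop A would lapse whatever the ALT. But the documents do not support the claim as a finding. The bullets apply to subjects in general, so they also bind a switched woman while her values stay in range. No passage describes the course of bilirubin or transaminases after atazanavir is stopped, and nothing ties the transaminase part to atazanavir. Criterion 10 admits any woman with normal direct bilirubin, whatever her regimen.

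**Conclusion.** The contradiction between Section 4.2 (criteria 9 and 10) and Section 7.5.6 is real and should be corrected. With normal direct bilirubin, a woman can be eligible while her total bilirubin is 5–10 × ULN with Grade 2 ALT or AST, or above 10 × ULN. Section 7.5.6 requires discontinuation for both, in the second case once confirmed. This holds at every bilirubin ULN tried and does not rest on an assumed number of women.

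The statistical consequence is limited and of unknown size. It reaches discontinuations, and hence the tolerability comparison, and the secondary rate below 50 copies/mL at 0.43 points per woman. It creates no primary-endpoint event. Neither the size of the atazanavir stratum nor the number of women with such values is in the documents. That the stop persists more often in women who stay on atazanavir is plausible but not established, so no directional bias should be claimed.

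**What to change.** Reconcile criteria 9 and 10 in Section 4.2 with Section 7.5.6, so that one Screening or Day 1 result cannot be both admissible for entry and a required stop. In 7.5.6, state whether the rules apply to both arms and all regimens, and how values already present at entry are handled. Which threshold governs is for the sponsor's clinicians. The cost is a protocol clarification.

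Optionally, list any discontinuations in women who already met a 7.5.6 criterion at Screening or Day 1, by arm. This needs one flag from laboratory values already collected. It must be labelled post hoc and descriptive: SAP Section 2.2 reports the Week 48 analysis as done, and SAP Section 2.3 limits the final analysis to B/F/TAF. For the same reason, the wording change can no longer alter who was enrolled here; it settles how the text is read and prevents the conflict wherever the criteria are reused.

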#### **4.3. Exclusion Criteria**

Subjects who meet *any* of the following exclusion criteria are not to be enrolled in this study.

- 1) An opportunistic illness indicative of stage 3 HIV diagnosed within the 30 days prior to screening (refer to [Appendix 5](#))
- 2) Subjects experiencing decompensated cirrhosis (eg, ascites, encephalopathy, or variceal bleeding)
- 3) Have been treated with immunosuppressant therapies or chemotherapeutic agents within 3 months of study screening, or expected to receive these agents or systemic steroids during the study (eg, corticosteroids, immunoglobulins, and other immune- or cytokine-based therapies)
- 4) Current alcohol or substance use judged by the Investigator to potentially interfere with subject study compliance
- 5) A history of or ongoing malignancy (including untreated carcinoma in-situ) other than cutaneous Kaposi's sarcoma (KS), basal cell carcinoma, or resected, non-invasive cutaneous squamous carcinoma. Subjects with biopsy-confirmed cutaneous KS are eligible, but must not have received any systemic therapy for KS within 30 days of Day 1 and are not anticipated to require systemic therapy during the study

- 6) Active, serious infections (other than HIV-1 infection) requiring parenteral antibiotic or antifungal therapy within 30 days prior to Day 1
- 7) Participation in any clinical trial other than GS-US-236-0128, GS-US-292-0109, GS-US-292-0104, or GS-US-292-0111, including observational studies, without prior approval from the sponsor is prohibited while participating in this trial
- 8) Any other clinical condition or prior therapy that, in the opinion of the Investigator, would make the subject unsuitable for the study or unable to comply with the dosing requirements
- 9) Any known allergies to the excipients of GS-9883/F/TAF FDC, E/C/F/TAF, E/C/F/TDF, ATV, RTV, or FTC/TDF
- 10) Women who are pregnant (as confirmed by positive serum pregnancy test)
- 11) Women who are breastfeeding
- 12) Subjects receiving ongoing therapy with any of the medications in [Table 5-1](#) or [Table 5-2](#). Administration of any disallowed agent must be discontinued at least 30 days prior to the Day 1 visit and for the duration of the study
- 13) Acute hepatitis in the 30 days prior to study entry
- 14) Active tuberculosis infection

## 5. INVESTIGATIONAL MEDICINAL PRODUCTS

### 5.1. Randomization

Subjects will be assigned a screening number at the time of consent. **Randomization and Day 1 visit cannot occur until subject eligibility has been confirmed.**

Once eligibility has been confirmed and prior to or during the Day 1 visit the Investigator or designee will randomize the subject using the Interactive Web Response System (IWRS). Once a subject number has been assigned to a subject, it will not be reassigned to any other subject. The subject number assignment and randomization may be performed up to 3 days prior to the in-clinic Day 1 visit provided that all screening procedures have been completed and subject eligibility has been confirmed.

Subjects will be randomized in a 1:1 ratio to Treatment Group 1 or Treatment Group 2.

- **Treatment Group 1:** FDC of GS-9883 50 mg/emtricitabine 200 mg/tenofovir alafenamide 25 mg (GS-9883/F/TAF) administered orally, once daily, without regard to food (approximately n = 235)
- **Treatment Group 2:** Stay on baseline regimen (SBR), including E/C/F/TAF, E/C/F/TDF or ATV+RTV+FTC/TDF administered orally, once daily, with food (approximately n = 235)

The IWRS will assign study drug bottle numbers of open label FDC of GS-9883/F/TAF, open label E/C/F/TAF, open label E/C/F/TDF or open label ATV+RTV+FTC/TDF at each study visit for each subject.

Randomization will be stratified by the prior treatment regimen group (ie, E/C/F/TAF, E/C/F/TDF and ATV+RTV+FTC/TDF).

### 5.2. Description and Handling

#### 5.2.1. Formulation

##### 5.2.1.1. GS-9883/Emtricitabine/Tenofovir Alafenamide (GS-9883/F/TAF) Tablets

GS-9883 50 mg/emtricitabine 200 mg/tenofovir alafenamide 25 mg tablets are capsule-shaped, film-coated purplish-brown, debossed with "GSI" on one side of the tablet and "9883" on the other side of the tablet. Each tablet core contains 50 mg of GS-9883, 200 mg of emtricitabine, and 25 mg of tenofovir alafenamide. In addition to the active ingredients, the GS-9883/F/TAF tablets contain croscarmellose sodium, magnesium stearate, and microcrystalline cellulose. The tablet cores are film-coated with iron oxide red, iron oxide black, polyethylene glycol, polyvinyl alcohol, talc, and titanium dioxide.

5.2.1.2. Elvitegravir/Cobicistat/Emtricitabine/Tenofovir Alafenamide (E/C/F/TAF) Tablets

E/C/F/TAF tablets are capsule-shaped, film-coated green tablets and are debossed with “GSI” on one side of the tablet and “510” on the other side of the tablet. E/C/F/TAF tablets contain 150 mg of elvitegravir, 150 mg of cobicistat, 200 mg of emtricitabine, and 10 mg of tenofovir alafenamide. In addition to the active ingredients, the E/C/F/TAF tablets contain colloidal silicon dioxide, croscarmellose sodium, hydroxypropyl cellulose, lactose monohydrate, magnesium stearate, microcrystalline cellulose, and sodium lauryl sulfate. The tablet cores are film-coated with indigo carmine aluminum lake, polyethylene glycol, polyvinyl alcohol, talc, titanium dioxide, and yellow iron oxide.

5.2.1.3. Elvitegravir/Cobicistat/Emtricitabine/Tenofovir Disoproxil Fumarate (E/C/F/TDF, Stribild®) Tablets

E/C/F/TDF tablets are capsule-shaped, film-coated green tablets and are debossed with either “GSI” on one side and the number “1” surrounded by a square box on the other side, or “GILEAD” on one side and plain-faced on the other side of the tablet. E/C/F/TDF tablets contain 150 mg of elvitegravir, 150 mg of cobicistat, 200 mg of emtricitabine, and 300 mg of tenofovir disoproxil fumarate. In addition to the active ingredients, the E/C/F/TDF tablets contain colloidal silicon dioxide, croscarmellose sodium, hydroxypropyl cellulose, lactose monohydrate, magnesium stearate, microcrystalline cellulose, and sodium lauryl sulfate. The tablet cores are film-coated with indigo carmine (FD&C Blue #2) aluminum lake, polyethylene glycol, polyvinyl alcohol, talc, titanium dioxide, and yellow iron oxide.

5.2.1.4. Emtricitabine/Tenofovir Disoproxil Fumarate (FTC/TDF, Truvada®) Tablets

FTC/TDF tablets are capsule shaped film-coated blue and are debossed with “GILEAD” on one side of the tablet and the number “701” on the other side. FTC/TDF tablets contain 200 mg of emtricitabine and 300 mg of tenofovir disoproxil fumarate. Further information is available in the Prescribing Information for Truvada®.

5.2.1.5. Ritonavir (RTV, Norvir®) Tablets

RTV tablets, 100 mg, are ovaloid shaped film coated white and are debossed with “aNK” on one side and plain faced on the other side. Further information is available in the Prescribing Information for Norvir®.

5.2.1.6. Atazanavir (ATV, Reyataz®) Capsules

ATV capsules, 300 mg, have a red and blue body and have “BMS 300 mg” in white characters on the cap of the capsule and “3622” in white characters on the body of the capsule. Further information is available in the Prescribing Information for Reyataz®.

## **5.2.2. Packaging and Labeling**

5.2.2.1. GS-9883 50 mg/Emtricitabine 200 mg/Tenofovir Alafenamide 25 mg (GS-9883/F/TAF) Tablets

GS-9883/F/TAF tablets are packaged in white, high density polyethylene (HDPE) bottles. Each bottle contains 30 tablets, silica gel desiccant and polyester packing material. Each bottle is enclosed with a white, continuous thread, child-resistant polypropylene screw cap with an induction-sealed and aluminum-faced liner.

5.2.2.2. Elvitegravir 150 mg/Cobicistat 150 mg/Emtricitabine 200 mg/Tenofovir Alafenamide 10 mg (E/C/F/TAF) Tablets

E/C/F/TAF tablets are packaged in white, high density polyethylene (HDPE) bottles. Each bottle contains 30 tablets, silica gel desiccant and polyester packing material. Each bottle is enclosed with a white, continuous thread, child-resistant polypropylene screw cap with an induction-sealed and aluminum-faced liner.

5.2.2.3. Elvitegravir 150 mg/Cobicistat 150 mg/Emtricitabine 200 mg/Tenofovir Disoproxil Fumarate 300 mg (E/C/F/TDF, Stribild®) Tablets

E/C/F/TDF tablets are packaged in white, high density polyethylene (HDPE) bottles. Each bottle contains 30 tablets and a silica gel desiccant with or without polyester coil fiber. Each bottle is enclosed with a white, continuous thread, child-resistant polypropylene screw cap with an induction-sealed and aluminum-faced liner.

5.2.2.4. Emtricitabine 200 mg/Tenofovir Disoproxil Fumarate 300 mg (FTC/TDF, Truvada®) Tablets

Refer to commercially available Prescribing Information.

5.2.2.5. Ritonavir (RTV, Norvir®) Tablets

Refer to commercially available Prescribing Information.

5.2.2.6. Atazanavir (ATV, Reyataz®) Capsules

Refer to commercially available Prescribing Information.

All study drug(s) to be distributed to centers in the US and other participating countries shall be labeled to meet applicable requirements of the United States Food and Drug Administration (FDA), EU Guideline to Good Manufacturing Practice – Annex 13 (Investigational Medicinal Products), and/or other local regulations.

